#### **Unaffiliated Personnel**

List investigators, if any, who will be participating in this protocol but are not affiliated with New York State Psychiatric Institute or Columbia University. Provide: Full Name, Degrees and Affiliation. This project is a single-site trial.

## **Procedures**

To create the protocol summary form, first indicate if this research will include any of the following procedures

- Psychiatric Assessment
- ✓ Collection of Biological Specimens
- ✓ Medication Trial
- ✓ Use of Placebo or Sham Treatment
- ✓ Medication-Free Period or Treatment Washout
- ✓ Use of Investigational Drug or Device
- ✓ Internet-based Data Collection or Transmission

## Population

#### Indicate which of the following populations will be included in this research

- Medically and Psychiatrically Healthy Subjects
- ✓ Adults
- ✓ Adults over 50
- ✓ Substance Users

## **Research Support/Funding**

Will an existing internal account be used to support the project?

Yes

Describe internal account

U54DA037842-01 Shared Pharmacotherapeutic Strategies for Cannabinoid & Opioid Use Disorders Is the project externally funded or is external funding planned?

Yes

Select the number of external sources of funding that will be applicable to this study

## **Funding Source #1**

Is the PI of the grant/contract the same as the PI of the IRB protocol? No Who is the PI of the grant/contract? [name], MD Select one of the following The grant/contract is currently funded Source of Funding Federal Institute/Agency NIDA

Grant Name Shared Pharmacotherapeutic Strategies for Cannabinoid & Opioid Use Disorders Grant Number U54DA037842-01 Select one of the following Single Site Business Office RFMH Does the grant/contract involve a subcontract? Yes Subcontracted? To Name institution(s) Columbia University

## Lay Summary of Proposed Research

Lay Summary of Proposed Research

The proposed protocol is a double-blind, placebo-controlled **inpatient and outpatient study**, combining our inpatient model of cannabis withdrawal with our expertise in the clinical treatment of cannabis use disorder. We will enroll 80 patients seeking treatment for cannabis use disorder into **the inpatient phase** for 5 nights. After discharge from the inpatient phase, 12-weeks of outpatient treatment will be conducted. This **combined** design will provide a comprehensive understanding of clonazepam's effects on individuals with cannabis use disorder across a range of outcome measures while also testing the medication's ability to prevent relapse in cannabis-abstinent patients.

#### **Background, Significance and Rationale**

#### Background, Significance and Rationale

Cannabis use is increasing and numbers are likely to rise further with legalization (Hasin et al., 2015). Currently, approximately 24% of patients entering treatment for a substance use disorder have cannabis use disorder (CUD; SAMHSA, 2013), yet their outcome is poor (MTPRG, 2004; Budney et al., 2006; Kadden et al., 2007; Levin et al., 2011, 2015). There is a clear need for FDA-approved pharmacological options to improve cannabis treatment outcome.

The purpose of this study is to test the effects of the benzodiazepine, clonazepam, as a potential treatment for CUD. The rationale for testing a benzodiazepine is the following: Cannabis withdrawal is, in part, characterized by symptoms such as anxiety and disordered sleeping (Haney et al., 1999, 2005; Budney et al., 2004), and clonazepam is efficacious and used therapeutically to treat both of these symptoms. Although benzodiazepines have the potential for abuse, clonazepam has a long half-life and is less reinforcing that fast-onset benzodiazepines (alprazolam, lorazepam) so was selected to be a time-limited treatment to facilitate the transition from regular cannabis use to abstinence.

Nonetheless, clonazepam is a controlled substance, and its administration to patients with a substance use disorder requires careful monitoring and minimization of the potential risks for misuse and physiological dependence. During the inpatient study period, study medication will be distributed on a single dose basis. During the outpatient period, study medication (clonazepam vs. placebo), will be distributed at weekly intervals and pill counts and biological measures of medication compliance (e.g., quantitative riboflavin) will be performed. The overall time period of potential exposure to clonazepam will be 8 weeks, with a 4 week time medication-free observation period following taper and discontinuation of study medication. These study features should minimize the risk of exposing individuals with CUD to clonazepam.

In order to most fully characterize the effects of clonazepam in patients seeking treatment for CUD, we have developed a novel **inpatient and outpatient study, combining our inpatient human laboratory model of cannabis withdrawal with our expertise in the outpatient treatment of CUD**. We will enroll patients seeking treatment for CUD into our inpatient laboratory for 5 nights, where we will initiate medication administration and test the influence of clonazepam on (1) cannabis withdrawal (mood, sleep, cannabis craving, food intake), ratings associated with medication abuse liability, cognitive performance, and (2) relapse to cannabis use after patients (now abstinent from cannabis) leave the inpatient setting maintained on clonazepam (or placebo) for 8 weeks (with a 4-week, medication-free follow up). This **combined** design will provide a comprehensive understanding of clonazepam's effects on individuals with cannabis use disorder across a range of outcome measures (safety, abuse liability, withdrawal symptoms) while also testing the medication's ability to prevent relapse in cannabis-abstinent patients.

## **Specific Aims and Hypotheses**

#### Specific Aims and Hypotheses

#### Primary Outcome Measure:

(1) Cannabis withdrawal (mood, sleep quality and duration, food intake)

(2) Cannabis relapse defined as (1) time to any MJ use as recorded by the timeline follow back method and

confirmed by urine metabolite levels, or (2) time to dropout, whichever comes first, and (3) medication compliance (% of pills taken) or time to discontinuation. Participants who relapse will continue in the trial to obtain secondary outcome measures.

## Secondary Outcome Measures:

(1) Abuse liability (medication liking, desire to take again)

(2) Cognitive task performance

(3) Side effects and tolerability.

## **Description of Subject Population**

#### Sample #1

Specify subject population Adults with CUD Number of completers required to accomplish study aims 60 Projected number of subjects who will be enrolled to obtain required number of completers 80 Age range of subject population 18-65

Gender, Racial and Ethnic Breakdown

Based on on-going research, it is expected that 20-30% of applicants will be female and 30% will have an ethnic identity of Hispanic. In terms of race, 30-40% are estimated to be Caucasian, 60-70% African American, and 5% Native American, Asian and Pacific Islanders, Eskimos, or Aleuts. Description of subject population

Description of subject population

We plan to enroll 80 participants into the study who meet criteria for current CUD and all other study criteria.

## **Recruitment Procedures**

Describe settings where recruitment will occur

The project will be completed at the inpatient unit at NYSPI and Substance Treatment and Research Services (STARS) of the Division on Substance Abuse (STARS Downtown) situated on [name].

How and by whom will subjects be approached and/or recruited?

Screening for this study will be covered by the Substance Treatment and Research Service (STARS) umbrella screening protocol #6582R (PI: [name]). Trained research assistants and administrative assistants under the supervision of the principal investigator conduct the initial phone screening. Under protocol #6582R, patients who contact STARS interested in research trial participation are informed that they will be asked questions of a personal nature and asked to provide verbal consent for such questions. A "phone screen" form is completed by the phone screener, which asks basic demographic

information, contact information (for scheduling purposes) and description of substance use to determine whether an inperson evaluation appointment is appropriate. Individuals are also informed that if they make an initial screening appointment this "phone screen" information will be forwarded to the clinician to facilitate the first meeting.

All patients will receive an explanation of the study risks, benefits, treatments, procedures, and option for alternative treatments. Patients who wish to participate will be asked to sign the treatment consent form following resolution of any questions and clear indication that they understand the nature of the study and consent form.

How will the study be advertised/publicized?

We will recruit individuals with CUD through newspapers, radio and public service announcements coordinated by the NYSPI Public Relations Office. This method has proven successful in several clinical trials at STARS. All advertisements will be sent to the Institutional Review Board for approval. The first phase of recruitment is a structured telephone interview when the initial contact is made. Individuals interested in receiving treatment for CUD will be asked to come to STARS for additional screening as per protocol #6582R. Those patients who meet criteria for CUD and all other inclusion/exclusion criteria will be asked if they are interested in participating in the study.

Do you have ads/recruitment material requiring review at this time? No

Does this study involve a clinical trial?

Yes

YOU MUST REGISTER AT ClinicalTrials.gov IMMEDIATELY UPON RECEIPT OF IRB APPROVAL AND PRIOR TO ENROLLMENT OF THE FIRST SUBJECT. YOU WILL BE PROVIDED WITH A NCT REGISTRATION NUMBER ON REGISTRATION. PLEASE REVISE THIS SECTION OF THE PROTOCOL SUMMARY FORM TO INCLUDE THE NCT NUMBER AND RE-SUBMIT AS AN AMENDMENT TO THE IRB.

## **Concurrent Research Studies**

Will subjects in this study participate in or be recruited from other studies?

Yes

Describe concurrent research involvement

Screening for this study will be covered by the Substance Treatment and Research Service (STARS) umbrella screening protocol #6582R (PI: [name]). Trained research assistants and administrative assistants under the supervision of the principal investigator conduct the initial phone screening. Under protocol #6582R, patients who contact STARS interested in research trial participation are informed that they will be asked questions of a personal nature and asked to provide verbal consent for such questions. A "phone screen" form is completed by the phone screener, which asks basic demographic information, contact information (for scheduling purposes) and description of substance use to determine whether an inperson evaluation appointment is appropriate. Individuals are also informed that if they make an initial screening appointment this "phone screen" information will be forwarded to the clinician to facilitate the first meeting.

#### **Inclusion/Exclusion Criteria**

Name the subject group/sub sample Adults with CUD Create or insert table to describe the inclusion criteria and methods to ascertain them

1) Meets DSM 5 criteria for CUD of at least moderate severity ( $\geq$  4 symptoms) and is seeking treatment for cannabis use. Clinical interviews (telephone, psychologist, physician)

2) Reports using cannabis an average of 5 days per week over the past 4 weeks

Timeline Follow-back procedure modified for marijuana (MJ-TLFB); urinary THC-COOH > 100 ng/mL Legal identification

3) 18-65 years of age

Create or insert table to describe the exclusion criteria and methods to ascertain them

1) Individuals with a lifetime DSM-5 diagnosis of
schizophrenia, schizoaffective disorder, or bipolar disorder

2) Individuals meeting current DSM-5 criteria for any other psychiatric disorder that may, according to the investigator's judgment, require either pharmacological or non-pharmacological intervention over the course of the study

3) Participants taking psychotropic medication

4) Known history of allergy, intolerance or hypersensitivity to benzodiazepines

5) Episodic or chronic use of benzodiazepines

6) Pregnancy, lactation, or failure to use adequate contraceptive methods (condoms, diaphragm, birth control pill, IUD) in female patients who are currently engaging in sexual activity with men.

7) Unstable medical conditions, such as poorly controlled hypertension, which might make participation hazardous

8) Participants with a current DSM-5 diagnosis of an alcohol of substance use disorder (abuse or dependence) other than cannabis or nicotine use disorder

MINI International Neuropsychiatric Interview for DSM V and psychiatric assessment

MINI International Neuropsychiatric Interview for DSM V and psychiatric assessment

Psychiatric assessment Psychiatric assessment, medical history, physical examination, and serum and urine laboratory testing

MINI International Neuropsychiatric Interview for DSM 5 and psychiatric assessment, urine toxicology; urine toxicology

Clinical interview, Medical history, and serum HCG

Medical history, physical examination, electrocardiogram, and serum and urine laboratory testing MINI International Neuropsychiatric Interview for DSM 5 and psychiatric assessment, urine toxicology,

	breathlyzer
9) Are legally mandated to participate in a substance use disorder treatment program	MINI International Neuropsychiatric Interview for DSM 5 and psychiatric assessment
10) Increased risk for suicide	MINI International Neuropsychiatric Interview for DSM 5 and psychiatric assessment
11) Current parole or probation	Self-report during interview
12) Recent history of significant violent behavior	Clinical interview
13) History of current of past diagnosis of glaucoma	Medical history, physical exam
14) History of benzodiazepine or other sedative hypnotic use disorder	MINI International Neuropsychiatric Interview for DSM 5 and psychiatric assessment

## Waiver of Consent/Authorization

Indicate if you are requesting any of the following consent waivers Waiver of consent for use of records that include protected health information (a HIPAA waiver of Authorization) No Waiver or alteration of consent No Waiver of documentation of consent No Waiver of parental consent No

## **Consent Procedures**

Is eligibility screening for this study conducted under a different IRB protocol? Yes Indicate NYSPI IRB # 6582R Describe Study Consent Procedures Screening for this study will be covered by the Substance Treatment and Research Service (STARS) umbrella screening protocol #6582R (PI: [name]). Trained research assistants and

umbrella screening protocol #6582R (PI: [name]). Trained research assistants and administrative assistants under the supervision of the principal investigator conduct the initial phone screening. Under protocol #6582R, patients who contact STARS interested in research trial participation are informed that they will be asked questions of a personal nature and asked to provide verbal consent for such

questions. A "phone screen" form is completed by the phone screener, which asks basic demographic information, contact information (for scheduling purposes) and description of substance use to determine whether an inperson evaluation appointment is appropriate. Individuals are also informed that if they make an initial screening appointment this "phone screen" information will be forwarded to the clinician to facilitate the first meeting.

Indicate which of the following are employed as a part of screening or main study consent procedures ✓ Consent Form

## **Study Procedures**

Describe the procedures required for this study

*Study Participants*: Participants will be 80 men and nonpregnant women with CUD who report using cannabis a minimum of 5 days per week over the past 28 days. The minimum threshold of a near-daily pattern of cannabis use will select a population with moderate-to-severe CUD. This level of severity is consistent with the sample in our previous clinical trial (Levin et al. 2011), and, we suspect, typical of individuals with CUD who seek treatment. This sample is less likely to achieve abstinence spontaneously or in response to non-medication aspects of the trial (e.g., general therapeutic support), and thereby minimize the placebo response rate. Selecting for near-daily cannabis users will also prevent a "floor effect" (i.e., participants using cannabis infrequently at baseline would be unlikely to demonstrate significant improvement).

**Inpatient phase**: Patients seeking cannabis treatment will move into the inpatient unit at NYSPI for 5 nights. On move-in day, participants will only receive the PM capsule administration; all capsules will be given under observation and will be double blind. During the next 4 days (days 2-5; Table 1), we will measure medication effects on cannabis withdrawal, including measures of mood, cannabis craving,

objective and subjective measures of sleep, and food intake in our Outpatient Marijuana Laboratory. Cannabis relapse measures will begin following discharge on day 6.

**Outpatient phase**: After discharge from the inpatient phase, 12-weeks of outpatient treatment will be conducted (Table 2). Study visits will occur twice weekly. One visit per week will be with the research psychiatrist for a Medical Management session to perform study assessments and to monitor medication effects and compliance. Participants will have a manual-guided (Pettinati et al. 2005) supportive behavioral treatment session with the research psychiatrist each week. This psychosocial intervention facilitates compliance with study medication and other study procedures, promotes abstinence from cannabis and other substances, and encourages mutual-support group attendance. The second visit each week will be for vital sign monitoring, urine toxicology and completion of self-report measures. Participants will be given cash incentives contingent on study visit attendance and completing other study procedures with the objective of achieving a high treatment adherence.

We will emphasize at each visit the importance of not stopping medication use abruptly. If participants wish to stop or use less medication at any point, we will initiate a taper with them. This outcome will be part of our secondary endpoint (medication adherence and tolerability).

*Medication:* Clonazepam and matching placebo will be prepared by our pharmacy at the NYSPI, packaged in matching gelatin capsules with lactose filler in each capsule. The research pharmacist, who has no contact with patients, is the only non-blind member of the research team. At each weekly visit the psychiatrist orders the dose of double-blind medication for the coming week according to the schedule (Table 2). The psychiatrist will adjust the dose according to tolerability. Clonazepam or matching placebo will be given in a fixed-flexible dose schedule with clonazepam dose titrated to 2mg per day or the maximum tolerated dose.

Clonazepam or matching placebo will be taken twice per day in the morning and in the evening. The medication will be packaged in gelatin capsules with lactose filler plus 12.5mg of riboflavin. Clonazepam or matching placebo are given in a "fixed flexible" dose schedule with the dose titrated to 2mg per day or the maximum tolerated dose.

If a patient does experience any uncomfortable side effects, the dose will not be raised, and if necessary, the dose will be lowered. If the patient cannot tolerate at least 0.5mg/day of clonazepam, the medication will be discontinued.

Planned/unplanned absences that would require the patient to be given more than one week worth of medications will be considered on a case-by-case basis. In the case of unplanned absences, up to one week of medication can be shipped via Fedex with signature upon receipt. This will allow patient who miss their scheduled appointments to remain on stable medication.

*Medication Taper*: During week 8, study medication will be tapered gradually to off (see table 2). This gradual discontinuation of study medication will minimize the discontinuation effects for participants exposed to clonazepam over the prior 7-week study period. For individuals exposed to clonazepam (a BZD with a long half-life) for a seven week period, a one week taper of study medication will be adequate to avoid the risk of physiological withdrawal. Participants will be monitored for the development of BZD withdrawal during and after the taper period, and will be managed clinically if significant withdrawal

symptoms emerge. It is unlikely that the length of time participants are exposed to clonazepam during the protocol will result in the development of physiological dependence that makes discontinuation difficult. However, there may be cases where participants due experience difficulty with the length of the taper schedule. If clinically significant withdrawal symptoms emerge during the taper, the taper may be extended for a second week based on clinical judgment by the study psychiatrist.

We will evaluate the adequacy of the double-blind by asking patients which treatment drug they think they are receiving. The blinded nurse will also be asked to report which drug s/he thinks each patient is taking. The research staff that administers medication and/or conducts interviews and assessments will be blind to medication condition, urine toxicology results, and medication blood levels during the course of the 12-week trial. The non-blinded pharmacist will be the only ones who have access to this information during the trial. However, a sealed envelope will be kept in the locked office if the Principal Investigator needs to break the blind in an emergency situation. At the completion of the 12 week trial, or at the conclusion of the patient's involvement in the trial (if they do not complete all 12 weeks), patient will learn their treatment assignment.

The medication capsules will contain riboflavin. This non-harmful substance will allow the clinic to verify that the study medication is being taken correctly and absorbed by the body. The urine samples obtained twice per week will be examined for riboflavin. In addition, folic acid in the form of a 1mg "pill" will be added to all placebo capsules in an attempt to improve the blind. The patient will receive up to 2mg of folic acid daily. Patients will receive medication in non-childproof packaging.

*Medication Adherence Enhancement*: We will use a combination of the quantitative fluorometric riboflavin determination method developed by our research group (Herron et al. 2013), timeline followback interview, and pill count with a weekly financial incentive (\$10) for medication bottle return to both enhance and measure medication adherence. Note, participants will be instructed to take their morning capsules and come to the clinic within 6-8 hours to ensure that riboflavin levels will be detectable.

Assessment of Side Effects and Medication Compliance: The research nurse and psychiatrist will query about side effects related to the study medication. Reported side effects and other treatment emergent events since the past visit will be recorded; additionally, the severity of the side effect/treatment emergent event, the action taken, and the continuation or resolution of the side effect/treatment emergent event will be documented.

You can upload charts or diagrams if any Table 1 inpatient.pdf Table 2 outpatient med dosing.pdf

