## Blood and other Biological Samples

Please create or insert a table describing the proposed collection of blood or other biological specimens Approximately 20 ml of blood (4 teaspoons) will be drawn at the time of baseline assessment, weeks 4, 8, and study completion for routine analyses (hematology, blood chemistry (including liver function tests), and blood pregnancy test for women). They may be repeated during the study if clinically indicated. Approximately, 80 ml of blood will be drawn overall (i.e., baseline, weeks 4, 8, and study completion = 4 x 20 ml = 80 ml).

Quantitative urine toxicology screens for THC with Creatinine will be conducted at each visit (2 per week) and serve as an objective marker of current cannabis use.

HIV testing will be offered in order to determine the HIV status of all possible participants; participants may refuse if they do not want to be tested. Nursing staff will provide Pre and Post-test counselling to assist participants with any HIV+ results. Pre-HIV test counselling discusses the possibilities of a HIV+ test and the procedures after a positive HIV test is found. Post-HIV counselling assesses for suicidal and/or homicidal ideation, along with domestic violence issues. If a person tests positive for HIV, the research psychiatrist on staff with be notified and will do a secondary evaluation for necessity of immediate psychiatric care. Additionally the nursing staff will notify the department of health and provide a list of referrals for follow-up care.

A confirmatory HIV test will not routinely be done due to the accuracy of the saliva quick test, however if a participant tests positive using the saliva quick test a confirmatory blood test will immediately be done.

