#### **Outpatient Study Assessments**

Adverse Effects measures: The Systematic Assessment for Treatment and Emergent Events (SAFTEE; Johnson et al. 2005) adapted for clonazepam will be performed weekly to identify adverse symptoms. Benzodiazepine withdrawal measure: The Clinical Institute Withdrawal Assessment-Benzodiazepines (CIWA-B)(Busto, 1989) is a 22-item scale to assess the degree of benzodiazepine withdrawal. Cannabis Craving measure: The Marijuana Craving Questionnaire (MCQ) is a 47-item instrument (Heishman et al. 2001).

Columbia Suicide Severity Rating Scale: Will be used to monitor suicidality at baseline and twice a month during the study period.

Medical Evaluation and Monitoring: A medical history and physical exam will be performed during screening. Serum pregnancy testing will be performed during screening and urine pregnancy testing will be performed monthly during the study. Complete blood count, electrolyte, urinalysis and liver function tests will be performed during screening and monthly during the study. Height and weight will be measured and baseline body mass index (BMI) calculated during screening. Temperature, pulse, blood pressure, and weight will be measured at every study visit.

Cannabis Use Outcome measures: Cannabis use will be recorded by the timeline followback (TLFB) method (Litten and Allen 1992) modified for cannabis and confirmed by creatinine-normalized quantitative urine THC levels. Other substance (including nicotine and alcohol) use self-report data will also be gathered during the TLFB interview. Urine samples for quantitative urine THC levels and creatinine will be collected under directly-observed conditions during screening and at each study visit (twice weekly). Creatinine levels can be used to control for urine concentration variability and screen for adulterated samples. Creatinine-corrected quantitative urine THC levels will then be used to confirm self-reported cannabis use, using a method similar to that described by Preston et al. (Preston et al. 1997) for cocaine dependence, where an obvious pattern of new use (i.e., level more than doubles in the past two days) overrides a self-report of no use.

Cannabis Withdrawal measure: We will use the 22-item version of the Marijuana Withdrawal Checklist (MWC; Budney et al. 1999) that measures subject-rated severity as the primary outcome measure of withdrawal.

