## Table 3: Outpatient Study Assessments

	X once weekly; XX twice weekly	Screening	Baseline	Week 1	Week 2	Week 3	Week 4	Week 5	Week 6	Week 7	Week 8	Week 9	Week 10	Week 11	Week 12
	Medical History and Physical Examination	x													
	Pregnancy, serum	x													
	Pregnancy, urine		x				х				х				х
	Psychiatric Evaluation	x													
5	Serum Laboratory Examination	x					х				х				х
latic	Urinalysis	x					х				х				х
Medical Evaluation	Urine Toxicology	x	x	х	X X	x x	x x								
dical	Urine Fluorometry (quantitative riboflavin)			x	X X	X X	x x								
Med	Vital signs (weight, pulse, blood pressure, and temperature)		x	x	X X	x x	x x								
	CIWA-BZD									Х	Х	Х	Х		
	Clinical Global Improvement Scale (CGI)- Observer		x	х	x	x	х	х	x	x	х	x	х	x	x
	C-SSRS	x	x		x		х		х		х		х		х
	Hamilton Anxiety Scale (HAM-A)		x		x		х		х		х		х		х
Interview	MINI International Neuropsychiatric Interview	x													
ter	Structure Pill Count Interview			х	x	x	х	х	х	x	х	х	х	х	х
_	Systematic Assessment for Treatment and Emergent Events (SAFTEE)		x	x	x	x	x	x	x	x	x	x	х	x	x
	Timeline Follow-Back (TLFB)	x	x	х	x	x	х	х	х	x	х	х	х	х	х
	Treatment Services Review (TSR)		х	х	x	x	х	х	х	x	х	х	х	х	х
	Clinical Global Impression (CGI)-Self		x	х	x	x	х	х	x	х	х	х	х	х	х
Self- Report	Marijuana Craving Questionnaire (MCQ)		х	х	x	x	х	х	х	x	х	х	х	х	х
Se Rep	Marijuana Withdrawal Checklist (MWC)		x	х	x	x	х	х	x	x	х	х	х	х	х
	Pittsburgh Sleep Quality Index (PSQI)		х	х	х	х	х	х	х	х	х	х	х	х	х

Tabl	e 1: Inpatient F					
Day	1	2	3	4	5	6
Study Groups	Move-in	Witha	Irawal, cognition	, abuse liability		Move-out
Clonazepam (mg/day)	1.0	2.0	2.0	2.0	2.0	2.0
Placebo (mg/day)	0.0	0.0	0.0	0.0	0.0	0.0

Study Groups	Week 1 Days 6-7 (outpatient)	Weeks 2-7 Days 8-49 (outpatient)	Week 8 Days 50-51 (outpatient taper)	Week 8 Days 52-54 (outpatient taper)	Week 8 Days 55-56 (outpatient taper)	Week 9-12 Days 57-84 (outpatient obervations)
Experimental Group	clonazepam capsules 1 mg twice daily	Clonazeapam capsules 1 mg twice daily	Clonazepam capsules 0.5 mg QAM and 1 mg QHS	Clonazepam capsules 0.5 mg QAM and 0.5 mg QHS	Clonazepam capsules 0.5 mg QHS	No study medication
Placebo Group	Placebo capsules Twice daily	Placebo capsules twice daily	Placebo capsules twice daily	Placebo capsules twice daily	Placebo capsule QHS	No study medication

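### The benzodiazepine-withdrawal scale (CIWA-B) is fixed to weeks 7–10, so a one-week taper to off begun in weeks 2–5 gets no rating on it while it runs

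*Protocol*

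**What the plan says.** Protocol, Study Procedures, tells participants not to stop abruptly and then says: "If participants wish to stop or use less medication at any point, we will initiate a taper with them". It gives no length for such a taper and attaches no withdrawal rating to it.

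The Medication Taper paragraph of the same section places the planned taper in week 8, over one week, and adds: "Participants will be monitored for the development of BZD withdrawal during and after the taper period". It also allows a longer course: "If clinically significant withdrawal symptoms emerge during the taper, the taper may be extended for a second week".

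Protocol, Outpatient Study Assessments, names one instrument for this purpose. The CIWA-B "is a 22-item scale to assess the degree of benzodiazepine withdrawal"; no timing is given there. Timing comes only from Table 3, where the CIWA-BZD row is marked once weekly in weeks 7, 8, 9 and 10 and is blank at screening, baseline, weeks 1–6 and weeks 11–12.

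For blood tests, Blood and other Biological Samples provides: "They may be repeated during the study if clinically indicated". No similar clause is written for the CIWA-B. The SAP does not mention the scale.

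**The concern.** The scale is tied to the calendar, while the event it should measure can happen in any week. A patient who asks to come off drug in week 3 or 4 goes through the whole taper before the first scheduled CIWA-B.

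A specific scale has value here because the symptoms overlap. Under Risks/Discomforts/Inconveniences, the protocol lists dysphoria and insomnia for milder benzodiazepine withdrawal, and irritability, anxiety and disturbed sleep for cannabis withdrawal. General scales will not readily separate the two. The HAM-A, which might help, is scheduled only at baseline and in even weeks, so a taper in week 3 or week 5 has neither HAM-A nor CIWA-B in that week.

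At stake is the description of how patients come off clonazepam. The protocol counts early stopping or reduction within its adherence and tolerability endpoint and lists "Side effects and tolerability" as a secondary outcome. If Table 3 is followed as written, early taperers give CIWA-B scores only after their taper, sometimes weeks after. A summary by calendar week would pool them with patients tapering at that time. Withdrawal among those who stop early would then tend to be under-recorded on this scale.

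**Working it through.** The plan states no figure to reproduce; the check is a count of scheduled ratings against taper days.

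**Inputs**
- CIWA-B weeks: 7, 8, 9, 10 (Table 3).
- Week k covers days 7k − 6 to 7k. This matches Table 2: weeks 2–7 are days 8–49, and week 8 is days 50–56. Week 7 therefore starts on day 43.
- Early taper length: 7 days, to off. This is an assumption, borrowed from the week-8 taper.
- Doses are ordered at the weekly psychiatrist visit (Study Procedures). I assume the CIWA-B is done on the same weekday as that visit, except where stated.

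**Early taper, rating while it runs.** A taper starting on day S ends on day S + 6. It can meet a CIWA-B week only if S + 6 ≥ 43, that is S ≥ 37. The latest start in week 5 is day 35, ending day 41. So no start day in weeks 2–5 reaches a rating.

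Week 6 covers start days 36–42. If the taper starts at the weekly visit, it ends the day before the week-7 visit and is missed. If start weekday s and rating weekday d are left free, the week-7 rating (day 42 + d) falls inside a taper ending on day 41 + s only when d < s. That is 21 of the 49 combinations. A week-7 start always has one.

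**When the first rating then comes.** For a start at the weekly visit in week w on weekday d, the last dose is on day 7w + d − 1 and the first CIWA-B is on day 42 + d. The gap is 43 − 7w days.

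| Start week | Start days | Latest end day | CIWA-B while it runs | Last dose to first CIWA-B |
|---|---|---|---|---|
| 2 | 8–14 | 20 | none | 29 days |
| 3 | 15–21 | 27 | none | 22 days |
| 4 | 22–28 | 34 | none | 15 days |
| 5 | 29–35 | 41 | none | 8 days |
| 6 | 36–42 | 48 | none if started at weekly visit | 1 day |

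**If the early taper took two weeks instead.** It ends on day S + 13 and reaches week 7 only if S ≥ 30. Starts in weeks 2–4 (latest day 28, ending day 41) still get no rating on any start day; week-5 starts get none if begun at the weekly visit.

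**Planned and extended week-8 tapers.** Planned: last dose day 56, with ratings in week 7 (before), week 8 (during), and weeks 9 and 10 (after). Extended: last dose about day 56 + 7 = 63, with ratings in week 7 (before), weeks 8 and 9 (during), and week 10 (after). Both have four ratings. Those after the last dose fall from two to one.

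**Exposure.** A taper begun at the start of week 6 follows 35 days on drug, against 49 before the planned taper (35/49 = 71%).

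**The case against.** The strongest reply is that early taperers are neither unseen nor unrated. The psychiatrist assesses them weekly; SAFTEE, CGI and PSQI are weekly; vital signs are taken at every visit; and nothing forbids an unscheduled CIWA-B. Concentrating the scale where exposure is longest is defensible, since the protocol regards difficult discontinuation as unlikely. This stands, and it limits the point to one scale.

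Several stronger readings are tempting, and the documents do not support them:
- A reader might infer that early taperers drop out of the CIWA-B record. They do not: Table 3 schedules by week, with no condition on being on drug.
- A reader might infer that the protocol breaks its own promise of monitoring during and after the taper. That sentence stands in the paragraph on the week-8 taper, where Table 3 delivers it.
- A reader might treat every early reduction as a taper to off. The offer also covers using less, and a patient held on a lower dose still has the week-8 taper with its four ratings.
- A reader might infer that an extended taper falls short of a required number of ratings. No text requires two after the last dose; one is in effect exchanged for a second rating on taper.
- A reader might infer a biased endpoint or a diluted comparison of arms. Adverse effects are measured by SAFTEE, and no CIWA-B comparison is planned.

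What the reply does not answer is that no text ties the only withdrawal-specific scale to a taper the protocol itself offers.

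**Conclusion.** The point holds as a minor gap in safety assessment. Under Table 3 as written, a one-week taper to off has no CIWA-B while it runs if begun in weeks 2–5, whatever the day. The same is true in week 6 if the taper starts at the weekly visit and the scale is given on that weekday. What is lost is largest for weeks 2–4, where the first rating comes 15 to 29 days after the last dose, and smallest for week 6. An extended week-8 taper has one rating after the last dose instead of two, in patients already known to have withdrawal symptoms.

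The conclusion rests on the assumed early-taper length and on staff following the schedule without adding ratings. The number of early tapers is not given, so the number of patients affected cannot be stated. The relapse result, power and error rate are untouched.

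**What to change.** Add a footnote to the CIWA-BZD row of Table 3 and a matching sentence in Study Procedures. For any early taper to off, in both arms, give the CIWA-B:
- at the visit where the taper is ordered, or at the next visit if it starts between visits;
- once in each week of the taper (with visits twice weekly, the second visit of the week can serve);
- weekly for two weeks after the last dose.

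Keep weeks 7–10 for the planned taper, add week 11 when it is extended, and report the CIWA-B by time since taper start. Stating the intended length of an early taper in the same sentence would remove the assumption made here.

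The cost is about four extra 22-item forms for a one-week early taper (1 + 1 + 2), five for a two-week one (1 + 2 + 2), and one per extended taper, at visits already planned. No extra patients or visits are needed. One limit remains: a taper begun between visits will have no CIWA-B rating from before the first reduced dose.
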